## **BACKGROUND, RATIONALE, AND CONTEXT**

Interstitial cystitis (IC), also referred to as painful bladder syndrome (PBS), is a heterogeneous chronic disease of unknown etiology that impacts up to 8 million women in America. Patients suffer from vague pelvic pain that can be exacerbated by bladder filling, and is often associated with urinary frequency and urgency. Since Alexander Skene's inception of the term in 1887, research into the etiology and pathophysiology of this disease has not been successful in elucidating a specific mechanism, revealing more questions than answers. As a result, treatment is difficult. Although there are many oral, intravesicular, and procedural treatments available, many patients remain refractory and require a more substantial treatment. Onabotulinumtoxin A may be that treatment.

Onabotulinumtoxin A has long been considered an efficacious treatment for various bladder pathologies such as overactive bladder (OAB) and neurogenic bladder. For the treatment of IC current AUA guidelines list intradetrusor Onabotulinumtoxin A injections as a fifth-line treatment option with grade C evidence (observational studies that are inconsistent, have small sample sizes, or have other problems that potentially confound interpretation of data). This option is based upon six observational studies that demonstrated highly variable amounts of short and long efficacy rates (from 20% to 86% at 3 months). Since the release of these guidelines other studies have confirmed Onabotulinumtoxin A's efficacy. While prior studies demonstrated the efficacy of intravesicular Onabotulinumtoxin A as a treatment, they largely did not address the importance of injection location. With the majority of bladder nociceptor and parasympathetic fibers located in the trigone, it stands to reason that injections to this area should have a more significant effect on bladder pain than injections elsewhere. The purpose of this study is to identify the importance of injection location for intravesicular Onabotulinumtoxin A.

We hypothesize that injections into the trigone should be more effective in the treatment of IC than injections elsewhere in the bladder. The lack of evidence on this topic has been noted by several authors and is important to the understanding and future use of Onabotulinumtoxin A in the treatment of IC.

### **Objectives**

The purpose of this study is to evaluate the efficacy of intravesicular Onabotulinumtoxin A injections for the treatment of interstitial cystitis (IC). Specifically, we hypothesize that trigonal Onabotulinumtoxin A injections is an effective treatment for IC and will result in more subjective and objective symptom relief than posterior wall Onabotulinumtoxin A injections.

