### **Specific Aims**

Patients diagnosed as having refractory IC will receive a one time dose of intravesicular Onabotulinumtoxin A with injections randomly assigned to either the posterior wall or trigone. Patients will be evaluated for subjective IC symptoms and objective flow performance prior to treatment as well as 30 and 90 days. This will test the hypothesis that intravesicular Onabotulinumtoxin A is an effective treatment for IC and that injections to the trigone are more effective than injections elsewhere.

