## **MATERIALS AND METHODS**

### **Design**

This is a single center, prospective, randomized clinical trial. Subjects will consist of patients referred to the urology clinic at Wake Forest University Baptist Medical Center with interstitial cystitis for whom conservative management/oral medications have failed and Onabotulinumtoxin A is recommended. These patients will all have undergone evaluation by [name]: an expert in the management of pelvic pain syndromes who sees >300 new patients each year.

Upon initial evaluation all subjects will undergo assessment including history taking and physical examination, urinalysis, subjective symptom assessment using self-reporting questionnaires, and objective symptom assessment using uroflowometry as well as the measurement of post void residuals.

After initial assessment subjects will be randomized into either the control or experimental cohorts. Subjects will receive a single dose of PO ciprofloxacin prior to injection unless culture or allergies dictate to use a different antibiotic. Each group will receive a total of 100 units of botox spread out among 10 separate injections. Subjects in the control group will have 10 injections made about the periphery of the trigone.

Subjects in the experimental cohort will receive a one time dose of 100 units of Onabotulinumtoxin A diluted in 10 mL of preservative free normal saline and injected in 1.0 mL boluses in a set pattern across the upper aspect of the trigone of the urinary bladder. Meanwhile, those subjects randomized to the control cohort will also receive a one time dose of Onabotulinumtoxin A using the same dilution and number of boluses, but boluses will be administered at random sites on the posterior bladder wall (excluding the trigone). Post –treatment, subjects will remain at the site for at least 30 minutes for observation and will demonstrate their ability to void before leaving. All procedures will be performed using the facilities of Wake Forest Baptist Medical Center.

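### The protocol says the trial will evaluate, test and measure whether the drug works, but both arms receive it and only the injection site is randomised

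*Combined protocol and SAP*

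**What the plan says.** The combined protocol and SAP gives two purposes.

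- **Location.** Background, Rationale, and Context says: "While prior studies demonstrated the efficacy of intravesicular Onabotulinumtoxin A as a treatment, they largely did not address the importance of injection location". It then states: "The purpose of this study is to identify the importance of injection location for intravesicular Onabotulinumtoxin A".
- **Drug efficacy.** Objectives opens with "The purpose of this study is to evaluate the efficacy of intravesicular Onabotulinumtoxin A injections for the treatment of interstitial cystitis (IC". Its second sentence hypothesises that "trigonal Onabotulinumtoxin A injections is an effective treatment for IC and will result in more subjective and objective symptom relief" than posterior wall injection, so an absolute claim precedes the comparative one. Specific Aims says: "This will test the hypothesis that intravesicular Onabotulinumtoxin A is an effective treatment for IC", and adds the trigone comparison as a further part of the hypothesis. The follow-up paragraph of Design says the data will be analysed for efficacy as well as for the effect of location. Outcome Measure(s) ends by tying the flow and residual measurements to how effective treatment is.

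On treatment, Specific Aims gives every patient one dose of the drug "with injections randomly assigned to either the posterior wall or trigone". Design says: "Each group will receive a total of 100 units of botox spread out among 10 separate injections". It adds that "those subjects randomized to the control cohort will also receive a one time dose of Onabotulinumtoxin A", with the same dilution and number of boluses.

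The Analytical Plan names comparisons between groups and a regression for predictors, and leaves room for other inferential analysis. It names no before-after test and no benchmark.

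**The concern.** A trial can test whether a drug works only against something that is not the drug. Here the control cohort is active treatment at another site, so randomisation protects the question of where to inject and not the question of whether injection helps.

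What is at stake is the conclusion drawn at the end. If both arms improve equally, the trial cannot tell whether both sites work or neither does. Under the present Objectives and Specific Aims, that result could still be reported as a successful test of the drug. The support would be change from day 0, which mixes drug effect with placebo or procedure response and natural fluctuation. The Background describes the guideline's evidence as grade C, from six observational studies with three-month efficacy rates of 20% to 86%. Another uncontrolled series would not settle that question.

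**Working it through.** **1. Which comparison the sample size serves.** Inputs from Power Analysis: d = 0.95, α = 0.05, and β written as 0.80, read here as 80% power. The stated result is 19 per arm, 38 in total.

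- Normal approximation, two-sided: n = 2(1.960 + 0.842)² / 0.95² = 15.70 / 0.9025 = 17.4, so 18 per arm.
- Two-sample t-test (noncentral t), two-sided: n = 18.41, so 19 per arm and 38 in total. This matches the plan.
- One-sided t-test: n = 14.43, so 15 per arm. This does not match.

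The plan's figure is thus a two-sided comparison of two arms. With the 20 per arm in Sample Size and Randomization, power is 0.833.

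**2. What that comparison can see.** Let c be the non-specific improvement (placebo, procedure, natural course), assumed equal in both arms, and let T and P be the drug's own effects at the trigone and posterior wall. Expected change is c + T in one arm and c + P in the other. The difference is (c + T) − (c + P) = T − P, so c and any drug effect shared by both sites cancel.

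Results for 20 per arm, normal change scores with SD 1, two-sided t-test at 0.05:

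| T | P | T − P | Probability of rejection |
|---|---|---|---|
| 0 | 0 | 0 | 5% |
| 0.5 | 0.5 | 0 | 5% |
| 0.95 | 0.95 | 0 | 5% |
| 2.0 | 2.0 | 0 | 5% |
| 0.95 | 0 | 0.95 | 83% |
| 1.95 | 1.0 | 0.95 | 83% |
| 0 | −0.95 | 0.95 | 83% |

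The equality within each block follows from the algebra. Simulation with 200,000 runs per row gave 4.95% to 5.05% in the first block and 83.2% to 83.5% in the second; that spread is simulation noise.

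**3. What change from day 0 can see.** The mean change in the trigone arm estimates c + T, not T. With 20 patients its 95% CI half-width is 2.093 / √20 = 0.47 SD of change. That interval describes c + T; more patients would narrow it without separating the two parts.

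The documents give no value for c. As an illustration only, suppose the drug does nothing and c is 0.2, 0.3, 0.5 or 0.8 SD of change. A paired two-sided 5% test would then be significant with probability 0.14, 0.25, 0.56 or 0.92 in one arm of 20, and 0.23, 0.46, 0.87 or above 0.99 in all 40. The plan names no such test, so these are not error rates of the plan.

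**4. Search for another comparator.** Sample Size and Randomization mentions the current patient population, but only as the source of the chosen number. Human Subjects Protection mentions age and gender matching, but no matched group is described. Neither supplies a control.

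**The case against.** The sponsor can say that an active comparator is legitimate, that location is the real question, and that day 0, day 30 and day 90 data allow efficacy to be described. The first two stand for the location comparison. The third stands for description only. Keeping a before-after aim, openly labelled as uncontrolled, would be an acceptable alternative to deleting it.

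The Background is also not one-sided. Beside its statement that efficacy was shown, it is tentative about the drug, reports widely varying rates and cites later confirming studies. So the efficacy aim is not absurd; it is simply not one this design can meet.

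A reader might infer more than the documents support:

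- *That the randomised comparison says nothing about whether the drug works.* This is too strong. If the drug were inert at both sites, the test would reject 5% of the time; if it worked at the trigone alone by 0.95 SD, 83%. Barring procedure effects that differ by site, a trigone advantage is some evidence against a drug inert at both. It still does not show how much of either arm's change is due to the drug.
- *That the location comparison is biased.* It is not: the missing comparator affects both arms alike.
- *That regression to the mean is established by the entry scores.* Subject selection criteria requires above 10 on the ICSS or ICPI and above 10 on the PUF, but nothing shows where those cut-offs fall in this population. The schedule has one pre-treatment questionnaire, in the combined screening and day 0 column, while Exclusion Criteria refers to a screening visit. It is possible and cannot be sized.
- *That 0.95 is documented as a difference between sites.* Power Analysis speaks of a large treatment effect. Reproducing 19 per arm identifies the formula, not the meaning of d.

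**Conclusion.** The point holds as a mismatch between stated aims and design, and it should be corrected. The contrast has a 5% rejection rate for any effect shared by both sites, and 83% power for a 0.95 SD site difference whatever the absolute effects. An overall efficacy conclusion therefore has no controlled support.

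These percentages assume normal change scores with equal SD, the same non-specific response in both arms, β = 0.80 meant as power, and 0.95 read as a site difference. The cancellation itself needs only the equal non-specific response. The size of any before-after bias cannot be obtained from the documents.

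The defect is confined to the efficacy half of the aims. A reader might conclude that the trial needs a sham arm or that its design is invalid. Neither follows, because the location question set out in the Background can be answered without one.

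**What to change.** 1. **Objectives:** replace both sentences. Suggested text: *The objective is to compare trigonal with posterior wall injection of the study drug in patients with refractory IC. The hypothesis is that trigonal injection gives greater subjective and objective relief.* Add no time points. Posterior wall is carried over from the present section and is not a ruling on the control site.
2. **Specific Aims:** strike the clause saying the drug is effective for IC and keep the comparison of sites.
3. **Design, follow-up paragraph:** remove the efficacy phrase, so that the data serve to measure the impact of injection location.
4. **Outcome Measure(s):** replace the closing phrase on objective effectiveness with wording limited to comparing the two sites.
5. **Analytical Plan:** add: *Change from day 0 within each arm will be reported descriptively, as mean change with 95% CI. It will not be reported as evidence of efficacy, and no before-after test will be run for that purpose under the provision for other inferential analysis.*
6. **Design, a separate issue:** one sentence places the control injections around the edge of the trigone, and another places them at random posterior wall sites outside it. Both are active drug, so the point above is unaffected, but the two must be reconciled before the location result can be interpreted.

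The cost is wording. Enrolment, sample size, visits and endpoints do not change. The sponsor gives up an efficacy claim that the design cannot support.

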### **Specific Aims**

Patients diagnosed as having refractory IC will receive a one time dose of intravesicular Onabotulinumtoxin A with injections randomly assigned to either the posterior wall or trigone. Patients will be evaluated for subjective IC symptoms and objective flow performance prior to treatment as well as 30 and 90 days. This will test the hypothesis that intravesicular Onabotulinumtoxin A is an effective treatment for IC and that injections to the trigone are more effective than injections elsewhere.

## **MATERIALS AND METHODS**

### **Design**

This is a single center, prospective, randomized clinical trial. Subjects will consist of patients referred to the urology clinic at Wake Forest University Baptist Medical Center with interstitial cystitis for whom conservative management/oral medications have failed and Onabotulinumtoxin A is recommended. These patients will all have undergone evaluation by [name]: an expert in the management of pelvic pain syndromes who sees >300 new patients each year.

Upon initial evaluation all subjects will undergo assessment including history taking and physical examination, urinalysis, subjective symptom assessment using self-reporting questionnaires, and objective symptom assessment using uroflowometry as well as the measurement of post void residuals.

After initial assessment subjects will be randomized into either the control or experimental cohorts. Subjects will receive a single dose of PO ciprofloxacin prior to injection unless culture or allergies dictate to use a different antibiotic. Each group will receive a total of 100 units of botox spread out among 10 separate injections. Subjects in the control group will have 10 injections made about the periphery of the trigone.

Subjects in the experimental cohort will receive a one time dose of 100 units of Onabotulinumtoxin A diluted in 10 mL of preservative free normal saline and injected in 1.0 mL boluses in a set pattern across the upper aspect of the trigone of the urinary bladder. Meanwhile, those subjects randomized to the control cohort will also receive a one time dose of Onabotulinumtoxin A using the same dilution and number of boluses, but boluses will be administered at random sites on the posterior bladder wall (excluding the trigone). Post –treatment, subjects will remain at the site for at least 30 minutes for observation and will demonstrate their ability to void before leaving. All procedures will be performed using the facilities of Wake Forest Baptist Medical Center.

After the procedure subjects will be scheduled for clinical follow-up at 2 weeks for a measurement of post void residual and adverse event collection. At the day 30 and 90 day follow-up visits patients will again undergo evaluation including collection of adverse events, concomitant medications, history taking and physical examination, urinalysis, subjective symptom assessment using self-reporting questionnaires, and objective symptom assessment using uroflowometry as well as the measurement of post void residuals. At day 45 and day 60 we will call to verify if patient has had any adverse events or changes in concomitant medications. We will then analyze the data generated by these follow-up visits to measure the efficacy of Onabotulinumtoxin A injections for interstitial cystitis as well as impact of injection location, if any.

Procedures, Tests and Evaluations	Screening and Baseline Study Day 0 in Clinic	Week 2 Clinic visit	Day 30 Clinic Visit	Day 45 Phone call	Day 60 Phone call	Day 90 Clinic Visit
	Day 0	Day 14 ±3	Day 30 ±3	Day 45 ±3	Day 60 ±3	Day 90 ±3
Informed Consent	X					
Medical History/Demographics	X					
Medical History verification		X	X			X
Concomitant Medications	X	X	X	X	X	X
Inclusion/Exclusion Verification	X					
Physical Examination (PE)	X		X			X
Uroflowometry	X		X			X
Pregnancy Test	X a					
Antibiotic dose	X					
Post-Treatment Observation and Void	X b					
Urinalysis/Urine Culture	X		X			X
Questionnaires—PUF, O’Leary-Sant	X		X			X
Bladder Post-void Residual	X	X	X			X
IP injections	X					
AEs	X	X	X	X	X	X

- a. For subjects who are of child-bearing potential
- b. Subjects will remain at site on Day 0 after treatment for at least 30 minutes for observation. Subjects must also demonstrate their ability to void before leaving.

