### **Sample Size and Randomization**

Each study arm will consist of 20 subjects for a total study population of 40. This number was chosen using estimates of symptom relief using our current patient population as reference.

Patients will be randomized to either the control or experimental cohort using a computer generated randomization table. Providers will not be aware of the subjects' cohort status until immediately prior to injection.

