### **Power Analysis**

We expect that treatment will result in a large effect and as such have set an anticipated Cohen's  $d$  as 0.95. Using this value along with standard study values of  $\alpha=0.05$  and  $\beta=0.80$  we calculated a minimum total study group requirement of 38 subjects with 19 subjects in each arm.

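### The Design section gives two different injection sites for the control arm, and site is the only thing that is randomised

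*Combined protocol and SAP*

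**What the plan says.** The control site appears in four places in the combined protocol and SAP, and one of them disagrees with the rest.

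- Design, end of the paragraph on randomisation and antibiotic cover: "Subjects in the control group will have 10 injections made about the periphery of the trigone".
- Design, next paragraph, which sets out treatment in detail: control "boluses will be administered at random sites on the posterior bladder wall (excluding the trigone"). The same paragraph has the experimental dose "injected in 1.0 mL boluses in a set pattern across the upper aspect of the trigone of the urinary bladder".
- Objectives: trigonal treatment "will result in more subjective and objective symptom relief than posterior wall Onabotulinumtoxin A injections".
- Specific Aims: a single dose "with injections randomly assigned to either the posterior wall or trigone".

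The Design section also gives each arm 100 units in 10 injections and states that dilution and number of boluses are the same in both.

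**The concern.** With drug, dose, dilution and bolus count held equal, the location of the injections is the whole of the randomised comparison. An unclear control site is therefore an unclear comparator.

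The two descriptions are different instructions. One places boluses around an anatomical landmark; the other scatters them at random over a wall. They may overlap in part, but an operator cannot follow both in full.

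The risk follows from the protocol's own rationale. The Background expects more benefit from the trigone because most bladder pain and parasympathetic fibres are there. The experimental boluses go across its upper part. Control boluses around its edge would be nearer to that field than random posterior-wall boluses. If benefit depends on closeness to the trigone, the difference between arms shrinks. The comparison would remain randomised, but it would be trigone versus just outside the trigone, and not the posterior-wall comparison in the Objectives.

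**Working it through.** **Text comparison**

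| Section | Control site |
|---|---|
| Objectives | posterior wall |
| Specific Aims (allocation sentence) | posterior wall |
| Design, detailed treatment paragraph | random posterior-wall sites, trigone excluded |
| Design, preceding paragraph | around the edge of the trigone |

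Three statements agree and one does not. No other section repeats, explains or withdraws the odd one.

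**The plan's own sample size**

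Inputs from Power Analysis: d = 0.95, alpha = 0.05, power 0.80 (printed as beta). Sidedness is not stated. For a two-sample t-test with n per arm, the noncentrality parameter is d × √(n/2), with 2n − 2 degrees of freedom.

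- Two-sided: n = 18.41, rounded up to 19 per arm, 38 in total. This matches the plan exactly.
- One-sided: n = 14.43, rounded up to 15 per arm. This does not match, so two-sided is used below.

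Sample Size and Randomization plans 20 per arm. The noncentrality parameter is then 0.95 × √10 = 3.004 on 38 degrees of freedom, and power is 83.3%.

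**Illustration of dilution**

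Two assumptions are needed, neither of which the documents supply:

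1. d = 0.95 is the trigone versus posterior-wall effect. Power Analysis says only "We expect that treatment will result in a large effect" and ties the value to no site contrast.
2. A fraction f of that effect is lost when control boluses lie around the trigone, so the effective size is 0.95 × (1 − f).

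| Scenario | Effective d | Noncentrality (d × √10) | Power, 20 per arm |
|---|---|---|---|
| No loss | 0.95 | 3.004 | 83.3% |
| 10% lost in all controls | 0.95 × 0.90 = 0.855 | 2.704 | 75.0% |
| Half the controls affected, each losing 25% (mean 12.5%) | 0.95 × 0.875 = 0.831 | 2.629 | 72.6% |
| 25% lost in all controls | 0.95 × 0.75 = 0.7125 | 2.253 | 59.3% |
| 50% lost in all controls | 0.95 × 0.50 = 0.475 | 1.502 | 31.0% |

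Simulating the half-affected control arm as a mixture (200,000 runs) also gives 72.6%.

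The smallest d with 80% power at 20 per arm is 0.909, so the margin is 1 − 0.909/0.95 = 4.3% of the contrast. To restore 80% power, a 10% loss would need 23 per arm (22.48 rounded up) and a 25% loss 32 per arm (31.91 rounded up).

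**The case against.** The strongest reply is that the document largely settles the matter itself. The stray line is a summary; the paragraph after it is the working description, with dose, dilution, bolus volume and site for each arm, and it agrees with the Objectives and the allocation sentence in the Specific Aims. Placement around the trigone can also be read as outside it, which fits the exclusion of the trigone. This stands as far as intent goes: the posterior wall is meant. It does not remove the fault, because a ring outside the trigone is still not random posterior-wall placement, and the sentence remains a treatment instruction in current text.

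Three further points have weight.

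- The Specific Aims end with a broader hypothesis, trigone against anywhere else in the bladder, and the Background uses similar terms. Control boluses just outside the trigone would still test that. The mismatch is with the Objectives and the allocation sentence.
- Providers do not learn "cohort status until immediately prior to injection" which arm applies. That fixes when allocation is revealed; it does not show that operators would consult, or prefer, the stray line. With a single centre, divergent readings are less likely, though not excluded.
- The loss fractions are assumed, and the 4.3% margin reflects how close 20 per arm is to the required 19. It would apply to any source of attenuation. The power figures show sensitivity and do not show that harm is likely.

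**Conclusion.** The concern holds. The Design section gives two control sites in consecutive paragraphs, nothing reconciles them, and they bear on the only factor that is randomised. The posterior wall is the intended site.

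The fault is in the treatment instruction and leaves the sample-size calculation untouched: 38 as the minimum and 40 as planned both stand. The effect on power is conditional. It is zero if sites around the trigone behave like posterior-wall sites. If d = 0.95 is the trigone versus posterior-wall effect, losing 10% to 25% of it across the control arm would lower power from 83% to between 75% and 59%. The documents give no basis for choosing within that range. The correction should be made because the control treatment ought to have one definition and the repair is nearly free.

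**What to change.** Delete the sentence that places control injections around the trigone. The following paragraph already defines both arms fully and agrees with the Objectives and the allocation sentence in the Specific Aims. If a summary line is wanted there, it should say random sites on the posterior wall with the trigone excluded, keeping the element of random placement.

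A sensible addition is one line on the procedure form for the sites actually injected. The visit schedule lists the injections but no record of site. The form itself is not among the documents, so this may already be done.

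The cost is one sentence removed and at most one data item added. No patients, visits or procedures are added, and the sample size does not change.

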### **Outcome Measure(s)**

The primary outcome will be a measurement of subjective patient pain using the Pelvic Pain and Urinary Urgency Frequency (PUF) questionnaire and the O'Leary-Sant Symptom and Problem Indexes. Patients will be asked to complete this questionnaire prior to treatment administration and at 30 and 90 days post treatment. The PUF and O'Leary Sant are previously validated tools that have been used by numerous researchers to evaluate pelvic pain. Secondary outcomes will be objective data as to patient performance in uroflowmetry as well as measurement of post void residuals. Patients will

again undergo these assessments prior to treatment and at 30 and 90 days post treatment to assess objective treatment effectiveness.

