### **Analytical Plan**

Results will be analyzed initially using descriptive statistics. Comparison between groups will be done using chi square tests for proportions, and t-tests or ANOVA procedures for continuous variables. Regression analysis will be performed to identify independent outcome predictors. Other inferential statistical analysis will be conducted as appropriate.

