### **Estimated Study Timeline**

The study treatment duration is 90 days from first evaluation and treatment to final follow-up. We estimate that the total study time (including IRB approval, patient recruitment, treatment, and data analysis following treatment) to be approximately 1 year and 4 months.

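### After injection the primary scores are taken only at the Day 30 and Day 90 visits; patients who leave or miss Day 90 have no route to a later score, and new non-drug IC treatment is not explicitly asked about

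*Combined protocol and SAP*

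**What the plan says.** The Outcome Measure(s) section defines the primary outcome: "The primary outcome will be a measurement of subjective patient pain using the Pelvic Pain and Urinary Urgency Frequency (PUF) questionnaire", together with the O'Leary-Sant indexes. On timing it says: "Patients will be asked to complete this questionnaire prior to treatment administration and at 30 and 90 days post treatment". Neither post-treatment time is named as primary.

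The schedule table under Design agrees. The row "Questionnaires—PUF, O’Leary-Sant" is marked at Day 0, Day 30 and Day 90, and is blank at Week 2, Day 45 and Day 60. The Week 2 visit has another purpose: "subjects will be scheduled for clinical follow-up at 2 weeks for a measurement of post void residual and adverse event collection". For the two telephone contacts the text reads: "At day 45 and day 60 we will call to verify if patient has had any adverse events or changes in concomitant medications".

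Some information on later treatment is collected. Concomitant medications are marked at all six contacts, and medical history is verified at Week 2, Day 30 and Day 90.

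The Analytical Plan names chi-square tests, "t-tests or ANOVA procedures for continuous variables", regression, and other analyses as appropriate. It gives no rule for missing scores, withdrawal or a change of treatment. Follow-up ends at Day 90: "The study treatment duration is 90 days from first evaluation and treatment to final follow-up".

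**The concern.** The patients are refractory and under chronic management, and the Background itself points to alternatives: "Although there are many oral, intravesicular, and procedural treatments available, many patients remain refractory and require a more substantial treatment". The entry criteria limit earlier toxin and certain current drugs, but no section addresses other IC treatment after injection. Some patients may therefore start something new, or stop attending, in the 60 days between the two scored visits.

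Two gaps follow.

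- **Leavers.** A patient who leaves after Day 30, or misses the Day 90 visit, has no later score. The forms are self-completed, but the plan has no early-exit assessment and no way to return them without a visit. If the reason for leaving is related to how she is doing, the remaining Day 90 scores are a selected set.
- **New treatment.** A medication question can reach drug instillations and repeat toxin. A non-drug procedure is not explicitly asked about, and may surface only at the Day 90 history, without a reliable date. If new treatment narrows the Day 90 difference between sites, the report could not say fully how much treatment there was, when it began, or in which arm.

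Both gaps concern data that cannot be recovered once the trial has ended.

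**Working it through.** **1. The plan's own figure.** Inputs from the Power Analysis section: d = 0.95, alpha = 0.05, and 0.80, which is printed as beta but reproduces the sample size only when read as power. A two-sided two-sample t-test needs 18.41 per arm, rounded up to 19, so 38 in total. This matches the stated minimum. (A one-sided test would need 15 per arm, 30 in total, and does not match.) The Sample Size and Randomization section plans 20 per arm, which gives power 0.833.

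**2. Margin for loss.** 1 − 38/40 = 0.05. The planned 40 cover a 5% loss, or one patient per arm. No dropout rate is stated.

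**3. Lost Day 90 scores (assumed rates, equal in both arms, unrelated to outcome).** Same t-test, d = 0.95, with 20 × (1 − loss) per arm:

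| Loss | Per arm | Power | Randomised to keep 38: 38/(1 − loss) |
|---|---|---|---|
| 0% | 20 | 0.833 | 38 |
| 5% | 19 | 0.813 | 40 |
| 10% | 18 | 0.791 | 43 |
| 20% | 16 | 0.739 | 48 |
| 30% | 14 | 0.677 | 55 |

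This shows loss of precision only. Bias from outcome-related loss cannot be computed from the documents.

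**4. New treatment with all 40 scored (assumed rates, in the less effective arm only).** If a fraction p starts new treatment and closes a share c of the gap to the other arm, with the SD unchanged, the expected difference becomes d × (1 − c × p). Power is at 20 per arm:

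| p | d, half catch-up (c = 0.5) | Power | d, full catch-up (c = 1) | Power |
|---|---|---|---|---|
| 10% | 0.95 × 0.95 = 0.903 | 0.79 | 0.95 × 0.90 = 0.855 | 0.75 |
| 20% | 0.95 × 0.90 = 0.855 | 0.75 | 0.95 × 0.80 = 0.760 | 0.65 |
| 30% | 0.95 × 0.85 = 0.808 | 0.70 | 0.95 × 0.70 = 0.665 | 0.54 |

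Full catch-up is close to a worst case in patients already refractory to conservative and oral therapy. Switching in both arms would change the result again.

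**5. Which comparison is exposed.** Day 30 scores precede any change made after Day 30, so steps 3 and 4 apply to Day 90 only. Because neither time is named as primary, Day 90 cannot be set aside as secondary.

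**The case against.** The strongest reply is that two post-treatment assessments are ordinary for a 40-patient, 90-day trial, and that randomisation protects the comparison. Much of this stands.

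- A reader might infer that, once patients switch, the Day 90 difference can no longer be attributed to injection site. The documents do not support that. Patients are randomised, and a switcher's Day 90 score is a valid observation for the effect of assigned site regardless of later treatment. Unequal switching would itself be a consequence of site.
- A reader might also infer that poor results disappear from the less effective arm and the difference is pulled toward zero. That is one possibility. Satisfied patients may also skip a visit, and no section gives a reason or a rate for either.
- It would be too strong to say that later treatment goes unrecorded. Medications are asked about at every contact and history is checked again at Day 90. What is missing is an explicit, dated prompt for any new IC treatment.
- It would also be too strong to say that the plan drops patients who leave. The Analytical Plan is silent, and it leaves room for other analyses.
- Extra scores at Day 45 and Day 60 help only patients who change or leave after those calls. For someone who changes at Day 35, the last score before the change is still Day 30. A form read aloud by telephone may also bring in the caller's influence, and blinding of callers is not stated.

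The reply does not answer the leavers. No section gives them a way to supply a primary score, and none says how their absence will be handled.

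**Conclusion.** The point holds as a cheap improvement to data collection and analysis. It does not show that the trial's comparison is invalid. The Day 30 comparison is unaffected by later changes. At Day 90, scores of patients who leave or miss the visit would be absent, possibly in relation to outcome, and any dilution from new treatment could not be fully described.

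The size is unknown because the documents give no rate of loss or switching. Under the assumed rates, a 10% or 20% loss of scores takes power from 0.83 to 0.79 or 0.74. Switching by 10% to 30% of the less effective arm gives 0.79 to 0.70 with half catch-up and 0.75 to 0.54 with full catch-up. All these figures rest on the plan's d = 0.95, a two-sided t-test, and losses or switching of the assumed form. They are illustrations, not forecasts.

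**What to change.** 1. **Design section and schedule table: scores.** Accept PUF and O'Leary-Sant remotely, preferably as a self-completed returned form, from anyone who stops attending or misses Day 90. Optionally collect them at the Day 45 and Day 60 contacts as well. Record the mode of collection.
2. **Design section and schedule table: treatment.** At every contact, widen the medication question to any new IC treatment, including instillations, procedures and repeat toxin, with its date. This records what happens and restricts nothing.
3. **Analytical Plan.** Compare all randomised patients by assigned site using all available scores, for example with a repeated-measures model that includes baseline. Report new IC treatment by arm. Add a sensitivity analysis in which scores after new treatment are treated as missing within that model. This is preferable to carrying the last score forward, which would mix Day 30, 45, 60 and 90 scores although response may change over that time.

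The cost is a few minutes on calls already scheduled, an added form field and a short addition to the analysis text. The downside is that some scores will come in a different mode from the clinic forms, which is why mode should be recorded and self-completion preferred over reading the form aloud.
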